Forty-one patients were consented and enrolled as participants. Thirteen (31.7%) of the participants did not complete this investigation for the following reasons: seven requested pharmacological intervention during the experimental period and were withdrawn, one was diagnosed with Rocky Mountain Spotted Fever and withdrawn, and five were lost to follow-up. Twenty-eight participants (68.3%) completed the investigation. Analysis was performed for the 28 participants with completed data sets. Mean age was 46.4 years (standard deviation = 16) and participants were 78.6% female.

Study Materials

Participants completed the Dizziness Handicap Inventory (DHI), Headache Disability Inventory (HDI), and lifestyle scale (Table 1) prior to and again after lifestyle modification intervention. The DHI and HDI are 25-item self-report tools that examine impact of dizziness symptoms and headache symptoms on HRQOL. Lower total scores indicate less impact of the symptoms on HRQOL. The lifestyle scale was developed for this study to gain an understanding of self-perceived restful sleep, mealtime regularity, exercise, and avoidance of dietary triggers. Participants indicated their level of agreement with each statement using a 5-point Likert scale. Higher scores indicated better self-perceived compliance with the lifestyle component.

Procedures

Data were collected either paper/pencil or using an online Redcap survey, depending on participant preference and in-person COVID-related limitations. Participants completed the DHI, HDI, and lifestyle scale during a clinic appointment before and after the intervention. On average, participants completed post-intervention surveys after 105 days (standard deviation = 78.1).

Intervention

The intervention addressed four areas related to lifestyle modification that have been shown to be effective in at least some patients with VM or with migraine. These areas were restful sleep, mealtime regularity, exercise, and elimination of dietary triggers. The diagnosing clinicians provided a four-page handout (see supplemental digital content) with information about each area after their diagnosis and after the patient completed the informed consent process.

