For restful sleep, we provided helpful tips adapted from the National Institute on Aging. To bring focus to mealtime regularity, the handout provided informational statements that skipping or missing meals can lead to symptoms and the participant should prepare ahead to ensure they are eating on a schedule. We also encouraged participants to continue or resume a preferred exercise program or start some type of formal exercise. A sample walking program from the National Heart, Lung, and Blood Institute²⁵ was adapted and provided along with the caveat to only begin such a program if medically cleared. Finally, we combined information from published research¹⁶ and other publicly available resources to develop a comprehensive elimination list of potential dietary triggers. Participants were asked to follow this four-part intervention until follow-up, with an initial goal of at least 60 days.

Statistical Methods

Scores on the lifestyle scale were analyzed using linear mixed-effects models with two within-participant factors, Intervention (pre-intervention, post-intervention) and Lifestyle Factor (restful sleep, exercise, mealtime regularity, avoiding dietary triggers).

Scores on the two handicap inventories, DHI and HDI, were also analyzed using linear mixed-effects models with two within-participant factors, Intervention (pre-intervention, post-intervention) and Inventory (DHI, HDI). For all models, participant was included as a random factor. Models were constructed using the *lmer* function of the *lme* package in R and were analyzed using the *anova* function in base R. Significant main effects and interactions were evaluated using the *emmeans* function of the *emmeans* package. Pairwise comparisons were adjusted to account for false-discovery rates.

Inter-individual variability in pre- to post-intervention scores were analyzed by calculating change scores (subtracting post-intervention from pre-intervention scores [DHI and HDI] or subtracting pre-intervention from post-intervention scores [lifestyle scale]). Two linear mixed models were constructed, one for each inventory, with the change scores as the dependent variable. Independent variables were participant sex, age, and lifestyle change score for each lifestyle question. Models were constructed and analyzed with the *lmer* and *anova* functions, respectively.

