Finally, to determine individual participant post-intervention change, we compared pre- and post-total scores for the DHI and HDI. On the DHI, a change of 18 points is considered significant. For the HDI, a change of 29 points is considered significant.

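### The two-factor mixed models, as described, test every within-participant effect against one pooled residual, which is right for all of them only under sphericity

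*Combined protocol and SAP*

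**What the plan says.** The Statistical Methods section sets out two linear mixed models. The DHI and HDI scores are modelled together with "two within-participant factors, Intervention (pre-intervention, post-intervention) and Inventory (DHI, HDI"). The lifestyle scale is modelled with "Intervention (pre-intervention, post-intervention) and Lifestyle Factor (restful sleep, exercise, mealtime regularity, avoiding dietary triggers"). On the random part it says: "For all models, participant was included as a random factor". It describes no random slope, participant-by-factor term, other covariance structure, sphericity check or correction. It prints neither a model formula nor a degrees-of-freedom method.

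Follow-up contrasts are estimated marginal means from the same fits, for effects that were significant, and "Pairwise comparisons were adjusted to account for false-discovery rates".

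The Study Materials section describes the DHI and HDI as "25-item self-report tools that examine impact of dizziness symptoms and headache symptoms on HRQOL". The Design and Participants section says: "Analysis was performed for the 28 participants with completed data sets".

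**The concern.** A model fitted with lmer and a participant intercept alone has one residual variance. With complete, balanced data it gives the repeated-measures ANOVA in which every within-participant effect is tested against one pooled error. That error is the average of the variances of the orthogonal within-participant contrasts. It suits all of them only if those variances are equal. Equal SDs with equal correlations would guarantee this, but are not necessary. The 2 × 2 model does not escape: each effect has 1 df, but the three effects share one error.

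The introduction gives the purpose as the effect on dizziness and on headache, so the pre-post tests of DHI and of HDI answer it most directly. This model forces a common standard error on both. The interaction, which asks whether the two symptoms respond differently, uses the same error. If that test is badly underpowered, a non-significant result may be misread as similar benefit on both. A false-discovery-rate adjustment cannot repair a wrong standard error. Point estimates are unaffected, because the 28 data sets are complete.

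**Working it through.** **Inputs from the document.** n = 28; 2 × 2 scores for DHI/HDI and 2 × 4 for the lifestyle scale. The pooled residual df, if the usual residual df are used, are 3 × 27 = 81 and 7 × 27 = 189. A contrast tested alone has 27 df. There is no design figure to reproduce: no SD, correlation, alpha or power is given for these models.

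**Assumed inputs.** A two-sided 5% level, normal scores, and the correlations below, written a/b/c: same inventory over time / different inventories at the same visit / both different. The HDI:DHI SD ratio k is 1, 1.25 or 29/18. The last borrows the document's individual-change thresholds for illustration only; they are not SDs.

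**Formulas, 2 × 2 model** (DHI variance 1; normalised contrasts):
- Intervention: (1+k²)/2·(1−a) + k(b−c)
- Inventory: (1+k²)/2·(1+a) − k(b+c)
- Interaction: (1+k²)/2·(1−a) − k(b−c)
- Pre-post change: DHI 1−a; HDI k²(1−a)
- Pooled error m = mean of the first three; model SE / true SE = √(m / contrast variance)

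**Example, 0.7/0.4/0.3, k = 1.** The variances are 0.4, 1.0 and 0.2, so m = 1.6/3 = 0.533. The ratios are √(0.533/0.4) = 1.15, √(0.533/1.0) = 0.73 and √(0.533/0.2) = 1.63. For a single inventory's pre-post change the ratio is √(0.533/0.3) = 1.33.

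SE ratios at equal SDs (above 1 is conservative, below 1 liberal):

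| a/b/c | Intervention | Inventory | Interaction | DHI or HDI pre-post |
|---|---|---|---|---|
| 0.5/0.5/0.5 | 1.00 | 1.00 | 1.00 | 1.00 |
| 0.7/0.4/0.3 | 1.15 | 0.73 | 1.63 | 1.33 |
| 0.6/0.4/0.3 | 1.06 | 0.79 | 1.37 | 1.19 |
| 0.5/0.5/0.3 | 0.90 | 0.90 | 1.37 | 1.06 |
| 0.4/0.6/0.3 | 0.79 | 1.06 | 1.37 | 0.97 |

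**Unequal SDs.** For 0.4/0.6/0.3 with k = 29/18, k² = 2.596 and (1+k²)/2 = 1.798. The three variances are 1.562, 1.067 and 0.595, so m = 1.075. The HDI ratio is √(1.075/1.557) = 0.83 and the DHI ratio √(1.075/0.6) = 1.34: HDI is too liberal and DHI too conservative. Even with all correlations at 0.5, this SD ratio gives HDI 0.86 and DHI 1.39.

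**Simulated size at nominal 5%, before gating or adjustment, over the three SD ratios.**
- 0.7/0.4/0.3 and 0.6/0.4/0.3: DHI 0.1% to 2.1%, HDI 1.1% to 4.7%, interaction 0.2% to 0.8%, Inventory 12.0% to 15.5%.
- 0.4/0.6/0.3 (in order of k): Intervention 11.9%, 11.6%, 10.6%; HDI 5.6%, 8.3%, 10.5%; DHI 5.8%, 3.1%, 1.0%.
- Paired tests: 4.6% to 5.2%.

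**With gating and adjustment.** Follow-up is assumed after a significant Intervention or interaction test, with Benjamini-Hochberg over the two inventories.
- No true effect: HDI false positives at most 5.3%.
- DHI improves 0.6 SD, HDI unchanged, 0.4/0.6/0.3: HDI false positives 7.2% (k = 1.25) and 8.6% (k = 29/18), against 4.2% and 4.3% with paired tests. If follow-up is gated on the interaction alone, at most 4.0%.
- Both improve 0.4 SD, equal SDs: DHI power 47% against 72% paired (0.7/0.4/0.3), and 44% against 58% (0.6/0.4/0.3).

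**Interaction power** (DHI improves 0.4 SD, HDI unchanged, equal SDs): 20% against 63% paired (0.7/0.4/0.3), and 22% against 46% (0.6/0.4/0.3).

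**Lifestyle model, equal item SDs.** Now a/b/c are same item over time / different items at the same visit / both different. The contrast variances are: Intervention 1−a+3(b−c), Lifestyle Factor 1+a−b−c, interaction 1−a−b+c, single item 1−a. The pooled error is m = (Intervention + 3 × Lifestyle Factor + 3 × interaction)/7.
- 0.6/0.3/0.2: m = (0.7 + 3.3 + 0.9)/7 = 0.70. Ratios: Intervention 1.00 (size 5.1%), interaction √(0.70/0.3) = 1.53 (under 0.1%), single item √(0.70/0.4) = 1.32.
- 0.4/0.4/0.2: m = (1.2 + 2.4 + 1.2)/7 = 0.686. Ratios: Intervention √(0.686/1.2) = 0.76 (13.6%), interaction 1.31 (0.4%), single item 1.07.

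With equal item SDs, the single-item tests are conservative or nominal. Only the most variable item became liberal (9.2% and 11.6%), in two settings with unequal item SDs.

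**The case against.** - **The reading.** The text says participant was a random factor, not that nothing else was random. It is loose elsewhere: it also describes lmer fits to change scores with one value per participant, where a participant intercept cannot be separated from the residual. This stands as a limit. Still, participant is the only random term named, and a random intercept is the natural reading.
- **No result is shown to be wrong.** This stands. Sphericity can be neither confirmed nor excluded from the document.
- **The harm is modest if each inventory correlates best with itself.** This also largely stands. The pre-post tests are then conservative or near nominal, so a significant pre-post result would hold. The one clearly liberal test is the Inventory main effect, which compares overall DHI and HDI levels and does not bear on the purpose. Power of the overall Intervention test barely moves when both improve 0.4 SD at equal SDs: 85% against 90% (0.7/0.4/0.3) and 81% against 82% (0.6/0.4/0.3). The losses fall on the single-inventory and interaction tests.
- **False positives need special conditions.** The HDI figures of 7.2% and 8.6% require dominant same-visit correlation, a more variable HDI, and a true effect on DHI alone. The overall Intervention inflation also requires same-visit correlation to dominate.
- **Some power comparisons set a gated model against ungated paired tests.** This shifts the powers with both inventories improving by at most about 2 points.

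**Conclusion.** The concern holds on the random-intercept reading. One residual serves every within-participant test and is right for all of them only under sphericity, and nothing else in the document adds a slope or a correction. The size and direction of error in the actual data are unknown. Under the assumed covariances, the clearest harms are a very conservative interaction test and lost power for the separate dizziness and headache tests, or, where same-visit correlation dominates, an overall Intervention test at about twice its nominal size. If further random terms were fitted but not reported, the problem shrinks or disappears. This should be corrected, but it does not show that any finding is false. Confidence is medium.

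**What to change.** - Test each pre-post change (DHI, HDI, each lifestyle item) with its own paired analysis on 27 df. Keep the planned false-discovery-rate adjustment, and state whether follow-up still depends on a significant omnibus effect; the paired tests do not need that step.
- Test the overall Intervention effect on each participant's mean change.
- Test Intervention by Inventory as a paired comparison of DHI change with HDI change.
- Test Intervention by Lifestyle Factor on the four item change scores, with a Hotelling test (3 and 25 df) or a Greenhouse-Geisser-corrected repeated-measures ANOVA. Simulated size was 4.8% to 5.3% and 4.2% to 4.5% respectively.
- If a joint DHI/HDI model is kept, use an unstructured within-participant covariance with Satterthwaite or Kenward-Roger df, and print the formula. Adding random intercepts alone still gives DHI and HDI one common pre-post standard error.
- If the fitted models already had more terms than described, print their formula and df method.

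**Cost.** A re-run on data in hand, with 27 error df in place of 81 or 189. If sphericity does hold (0.5/0.5/0.5, equal SDs), unadjusted power for a 0.4 SD change in DHI alone falls from 55% to 53%. With adjustment, it is 40% for the gated model and 42% for ungated paired tests. An unstructured 8 × 8 covariance may be unstable with 28 participants, so change-score tests are the simpler route for the lifestyle scale.

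### The change-score models are specified as lmer mixed models with one row per participant, so they cannot be run as written, and the basis of the predictor tests is not stated

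*Combined protocol and SAP*

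**What the plan says.** Design and Participants fixes the analysis set: "Analysis was performed for the 28 participants with completed data sets". Under Study Materials and Procedures, each inventory is completed once before and once after the intervention, so a participant has one change score on the DHI and one on the HDI.

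Statistical Methods then describes the analysis of individual differences: "Two linear mixed models were constructed, one for each inventory, with the change scores as the dependent variable". The predictors are given as "Independent variables were participant sex, age, and lifestyle change score for each lifestyle question", and the software as "Models were constructed and analyzed with the *lmer* and *anova* functions, respectively".

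The paragraph before it, on the repeated-measures models, says "For all models, participant was included as a random factor" and "Models were constructed using the *lmer* function of the *lme* package in R and were analyzed using the *anova* function in base R". No other grouping factor is named anywhere. For the predictor tests the text gives no type of sums of squares, no order of entry, no denominator degrees of freedom and no source of p-values.

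**The concern.** A mixed model with a participant effect needs more than one outcome value from at least some participants. A change score, modelled separately for each inventory, leaves one per participant. The random effect is then indistinguishable from the residual, and the named function should refuse the model.

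The second gap is separate. What `anova` returns depends on the class of the fitted object, so naming it does not say which test was done. In a sequential test each predictor is adjusted only for those entered before it. In a partial test it is adjusted for all the others.

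These models ask which of sleep, meals, exercise and diet goes with improvement. All four were delivered together in one handout, so correlated changes are plausible, and with correlated predictors the two kinds of test can disagree. A reader cannot tell whether each component was tested adjusted for the other three.

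**Working it through.** **1. Rows per model.** Enrolled 41; not completing 7 + 1 + 5 = 13; analysed 41 − 13 = 28, and 28/41 = 68.3%, as the plan states. One change score per participant per inventory and one model per inventory give 28 rows and 28 participant levels.

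**2. Coefficients.** Intercept, sex, age and four lifestyle changes (one for each factor named in Statistical Methods) make 7. Residual df = 28 − 7 = 21. The two-sided 5% critical value of t on 21 df is 2.080.

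**3. Identifiability.** With one row each, Var(yᵢ) = τ² + σ², where τ² is the participant variance and σ² the residual variance. Only the sum enters the likelihood. On simulated data with this layout and the total variance held fixed, the REML log-likelihood was −85.941 whether τ² was 0%, 50% or 99.9% of the total.

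**4. Running it.** R with lme4 1.1.37, simulated data, 28 participants, six predictors:

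- With a participant random intercept, lmer stops: `number of levels of each grouping factor must be < number of observations`.
- With no random term, lmer stops: `No random effects terms specified in formula`.
- With the checks overridden, a fit is returned with participant SD 15.460 and residual SD 6.184. The squares are 239.01 + 38.24 = 277.25 (277.26 before rounding), which is the residual variance from `lm`, 277.26. Over the runs made, coefficients differed from `lm` by at most 3 × 10⁻¹³ and standard errors by at most 7 × 10⁻¹⁵.
- Stacking four rows per participant with the outcome repeated leaves no within-participant variation. The residual SD fell to 0.00015 and the fit did not converge.

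**5. What `anova` prints.** On the forced lme4 fit it gives F values and no p-value, and those F values equal the sequential F values from `lm` (for example sex 2.2602, age 0.2886). On an lmerTest fit it gives Type III tests with p-values on 21 df, equal to `drop1` on `lm`. The plan does not name lmerTest. Referring the statistic to a normal or chi-square distribution instead of t on 21 df would give a true size of 6.3% at a nominal 5%.

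**6. Size if the p-values were sequential.** The documents give no effect sizes, correlations or entry order, so these are assumed: residual SD 1, 78.6% female, age, and four equicorrelated lifestyle changes with unit variance, of which one is active. There were 20,000 simulated studies per setting. Percentage of studies in which an item with no effect of its own is significant at 5%, averaged over all 24 entry orders of the four items:

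| Active slope | r = 0.2 | r = 0.4 | r = 0.6 |
|---|---|---|---|
| 0.2 SD | 5.3 | 5.6 | 6.2 |
| 0.3 SD | 5.9 | 6.9 | 8.0 |
| 0.4 SD | 6.4 | 8.2 | 10.2 |
| 0.6 SD | 8.5 | 11.7 | 16.3 |

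Partial tests gave 4.8% to 5.2% throughout. Entry order drives the result. With the active item first, the sequential rate is about 5%. With a null item first and the active item last, it is 5.7/7.0/9.1% at 0.2 SD and 12.9/23.5/41.3% at 0.6 SD. With a random order, at least one of the four sequential verdicts differs from the partial verdict in 11.2/14.4/18.1% of studies at 0.2 SD and 22.4/34.3/49.3% at 0.6 SD.

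**7. Reach.** In the balanced pre/post models (28 × 2 × 2 and 28 × 2 × 4), sequential and Type III F values differ by at most 7 × 10⁻¹⁶, so the choice of test type does not matter there. The 18-point and 29-point individual comparisons use no model.

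**The case against.** The strongest reply is that nothing has been shown to go wrong. The estimates are those of ordinary regression, and no sentence says the tests were sequential. Plain lme4 prints no p-values, so sequential ones need an unstated step: `lm` in place of lmer, a Type I request, or calculation by hand from the printed F. The plan is already loose about software (it attributes lmer to a package called lme), so an unnamed lmerTest, with Type III defaults, is a plausible omission. This stands. It is why confidence that sequential tests were used is low, and why the point is minor.

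The percentages also need care. A first-entered sequential test answers an unadjusted question. At 0.6 SD and r = 0.6 the null item has an unadjusted slope of 0.6 × 0.6 = 0.36 SD, and the power to detect that slope is about 0.40, close to the simulated 0.413. The top figure is therefore mainly detection of a real unadjusted association. At r = 0.2 the same calculation gives 0.088 against 0.129, so some inflation remains. The verdict differences include the active item too: null items alone differ in 6.7–12.9% of studies at 0.2 SD and 15.6–36.4% at 0.6 SD. A differing verdict is not always a wrong one.

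Two smaller points are fair. The missing source of p-values touches the pre/post models as well. And the 21 df and the simulations assume one question per lifestyle factor.

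The statement about a participant random factor precedes the change-score paragraph and may cover only the earlier models. That does not rescue the text, because lmer also fails with no random term.

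**Conclusion.** The concern holds, as a minor point about a secondary analysis. Both change-score models are mis-specified as mixed models and will not run in lmer under default settings on either reading of the text. This rests only on one change score per participant per inventory, which follows from the described data collection. The numerical effect on the coefficients and their standard errors is nil.

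The basis of the predictor tests is not stated. If partial tests were used, no result changes. If sequential tests were used, verdicts on single components depend on entry order, to the extent shown by the simulations under their assumed effects and correlations. With lmerTest defaults those percentages do not apply. Confidence is high that the models cannot be run as written and that the test basis is missing, and low that sequential p-values were actually used.

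**What to change.** Replace the mixed-model description with one ordinary linear regression (`lm`) per inventory, one row per participant and no random effect, with 21 residual df if there is one score per lifestyle factor. Test each predictor adjusted for all the others (`drop1`, or Type II/III tests), and name the package and test type. Coefficients with 95% confidence intervals would also show the reader the size and precision of each association.

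The sponsor should state which tests were run. If they were partial, correct the wording only. If they were sequential, re-run the two models. The cost is one or two sentences, at most a short re-run, and no new data. The possible downside is fewer significant predictors.

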It is unsurprising that lifestyle modification would improve symptoms of VM. There is sufficient evidence in the literature that lifestyle modification is beneficial for non-VM forms of migraine that we will refer to collectively as migraine. Migraine symptoms have been shown to improve in 63-93% of patients through dietary interventions and in 48.9% of patients through cognitive behavioral therapy to treat insomnia. Conversely, missing meals or fasting has been reported to trigger migraines in as many as 57% of migraineurs. Finally, low-level physical activity and exercise has been shown to reduce migraine symptoms. However, avoidance of dietary triggers, restful sleep, mealtime regularity, and exercise have not yet been systematically investigated as a comprehensive approach to management of symptoms of VM.

More work is needed to prospectively determine the outcomes of lifestyle modification on VM. As noted, VM accounts for a large percentage of individuals affected by symptoms of dizziness and imbalance. It is also important to understand the effects of lifestyle modification on VM to assist with evaluation of other interventions, including pharmacological ones. The purpose of the current investigation was to prospectively evaluate the effects of common lifestyle modifications on symptoms of dizziness and headache in patients diagnosed with definite VM.

Materials and Methods

Design and Participants

Participants were recruited from patients seen for consultation for dizziness and/or imbalance in the John S. Odess Otolaryngology and Head and Neck Surgery Clinic. Consultations were provided by two nurse practitioners and one otolaryngologist. All clinicians were experienced in diagnosis and management of dizziness and imbalance including VM. All adult patients diagnosed with definite VM using the consensus criteria were eligible for inclusion. Patients who were determined to need pharmacological management at initial consultation were excluded.

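### No stated analysis tests whether overall lifestyle change tracks symptom change: the change-score models carry four separate item terms, with no total score and no joint test

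*Combined protocol and SAP*

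**What the plan says.** The introduction says that the four lifestyle areas "have not yet been systematically investigated as a comprehensive approach to management of symptoms of VM". It then gives the purpose as to "prospectively evaluate the effects of common lifestyle modifications on symptoms of dizziness and headache in patients diagnosed with definite VM". Under Intervention, every participant receives the same package: "Participants were asked to follow this four-part intervention until follow-up, with an initial goal of at least 60 days".

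Under Study Materials, lifestyle is measured by a scale made for this study: "Participants indicated their level of agreement with each statement using a 5-point Likert scale". No total score is defined.

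Statistical Methods then sets out four analyses:

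- a mixed model of the lifestyle scale by Intervention and Lifestyle Factor;
- a mixed model of DHI and HDI by Intervention and Inventory;
- two change-score models, one per inventory, presented as an analysis of variability between individuals: "Independent variables were participant sex, age, and lifestyle change score for each lifestyle question";
- individual change compared with 18 points (DHI) and 29 points (HDI).

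On numbers: "Thirteen (31.7%) of the participants did not complete this investigation", and "Analysis was performed for the 28 participants with completed data sets". False-discovery adjustment is stated for pairwise comparisons only.

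**The concern.** Of these analyses, only the change-score models connect how much a participant's lifestyle changed with how much that participant's symptoms changed. In them, each lifestyle coefficient describes one component with the other three held fixed. All four components came in one handout at one time, so their changes may well move together. If they do, each partial effect is imprecise, and four non-significant items can sit beside a clear overall relation.

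There is no control group, so the pre/post difference also absorbs regression to the mean, natural fluctuation and selective completion. The link between lifestyle change and symptom change is the nearest thing to dose-response evidence in this design. Read term by term, the models could suggest that lifestyle change explained nothing, or could credit one component by chance.

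**Working it through.** **No design figure to reproduce.** The documents state no power, alpha, effect size or correlation. The counts agree: 41 − 7 − 1 − 5 = 28; 13/41 = 31.7%; 22/28 = 78.6%, matching "participants were 78.6% female".

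**Inputs from the documents.** n = 28; 22 women and 6 men; predictors sex, age and four item changes.

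**Assumptions, not in the documents.** Two-sided 5% tests; normal scores; lifestyle R² of 0.20 to 0.40; common correlation ρ between item changes of 0 to 0.7; effects shared equally by all four components, or confined to one. The models are treated as ordinary regression, because with one change score per participant a participant random intercept cannot be separated from residual error. Item tests are taken as one mutually adjusted test per term; the plan does not spell out its anova output.

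**Degrees of freedom.** Four-item model: 28 − 7 = 21 residual. Total-score model (intercept, sex, age, total): 28 − 4 = 24.

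**Approximate information in each test, equal effects.**

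- Overall: λ = n·R²/(1 − R²) = 28 × 0.20/0.80 = 7.0. The total score spends this on 1 df, the joint test on 4 df. Non-central F power is 0.72 and 0.44. The simulated values below are a little lower, because the formula ignores sampling variation in the predictors and the adjustment for sex and age.
- Variance inflation per item: (1 + 2ρ)/[(1 − ρ)(1 + 3ρ)]. At ρ = 0.5 this is 2/(0.5 × 2.5) = 1.6.
- Each item: with equal effects, β² = R²/[4(1 + 3ρ)], so λ_item = λ(1 − ρ)/[4(1 + 2ρ)]. At ρ = 0 this is 7/4 = 1.75. At ρ = 0.5 it is 7 × 0.5/8 = 0.44. Correlation cuts the information in each item to a quarter and leaves the overall λ unchanged.

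**Simulated power, R² = 0.20** (3,000 runs per setting):

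| Effect pattern | ρ | At least one item, unadjusted | Joint 4-df test | Summed score |
|---|---|---|---|---|
| All four equal | 0 | 0.55 | 0.38 | 0.65 |
| All four equal | 0.5 | about 0.30 | 0.39 | 0.65 |
| All four equal | 0.7 | 0.23 | 0.37 | 0.64 |
| One only | 0 | 0.64 | 0.39 | 0.19 |
| One only | 0.5 | 0.49 | 0.40 | 0.45 |

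With equal effects and ρ = 0.5, R² from 0.20 to 0.40 gives 0.29 to 0.50 for at least one item, 0.39 to 0.83 for the joint test and 0.65 to 0.96 for the sum. In 43% to 50% of those runs the sum was significant and no item was.

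**Error rate of the any-of-four reading.** For independent tests, 1 − 0.95⁴ = 18.5%; simulated, about 17%. It is not a 5% overall test.

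**If the four items were FDR-adjusted** (R² = 0.30, equal effects), at least one is significant with probability 0.47, 0.23, 0.16 and 0.09 at ρ = 0, 0.3, 0.5 and 0.7. The joint test stays near 0.63 and the sum near 0.86 throughout.

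**The case against.** A reader might infer that the combined approach is never tested. The documents do not support that. Everyone received the whole package, and the Intervention factor in the DHI/HDI model tests average change under it. The 18- and 29-point comparisons add individual change, and the Intervention effect in the lifestyle-scale model tests overall lifestyle change. The gap is only in the link between the two kinds of change.

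A reader might also infer that a real association is likely to be missed. That depends on assumptions the documents cannot settle. With equal effects at R² = 0.20, the power for one pre-chosen item (20% at ρ = 0, 9% at ρ = 0.5) is not the chance that an association goes unseen, since all four terms are read. With uncorrelated changes and shared effects, at least one item is significant 55% to 88% of the time over R² of 0.20 to 0.40, above the joint test (38% to 81%). With one active component at zero correlation, it beats the sum easily. These points stand, with one limit: the any-of-four reading has about a 17% false-positive rate. Once FDR-adjusted, it is at or below the joint test in every setting examined, within simulation error.

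It is also fair that the models are presented as an analysis of variability between individuals, that asking which component tracks improvement is legitimate, and that the scale has no defined total. A sum added now would be post hoc, since the text reports completed work. All of this argues for adding an overall test beside the item model rather than replacing it.

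**Conclusion.** The point holds as a modest, inexpensive improvement. No stated analysis gives a single valid test of whether overall lifestyle change tracks DHI or HDI change. The loss is material if effects are shared and item changes correlate at about 0.5 or more: roughly 30% for any item unadjusted, against 40% (joint) and 65% (sum), at an assumed R² of 0.20. It is not general, and nothing in the documents shows which setting applies.

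Nor would a positive slope settle the comprehensive-approach question. It would be an observational association between self-perceived compliance and self-reported symptoms in an uncontrolled group of completers.

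**What to change.** For each inventory, keep the four-item model and add:

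- (a) a model of the change score on sex, age and one total lifestyle change score (sum or mean of the four items), reporting the slope with a 95% CI;
- (b) the joint 4-df test, comparing the four-item model with one holding sex and age only.

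Report both whatever the result, labelled as added, exploratory, observational associations. Fit them by ordinary regression, or explain how a participant random factor is identified with one row per participant. Reporting the correlations among the item changes would show how far the power concern applies here.

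Cost: one extra model and one model comparison per inventory, on data already collected. Downside: the equal-weight total is not a defined scale score, and it has only about 20% to 35% power (assumed R² of 0.20 to 0.40) if one component alone matters and item changes are uncorrelated. The joint test and the retained item model cover that case.
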